- h. As well the research staff member will ensure that the nurse adjusts the investigational system's MAP and SBP goals, if these are ordered to be changed during the protocol.
 - i. The Technical Observer will document any identifiable interventions of events that have any effect on the patient's blood pressure or heart rate. When the Technical Observer perceives any substantial changes in the subject's hemodynamics, a time-stamped annotation will be made for the perceived cause. The goal is to have these events documented with very precise temporal resolution, i.e., down to the precise minute that the events occur. The Technical Observer may ask the nurse to clarify what intervention is occurring; by protocol, Technical Observer will not ask this clarification if there is any perception that time-sensitive interactions being delivered and/or if the nurse is discussing patient management with any other clinical team member. The Technical Observer will never suggest intervention or recommend any clinical care for the patient.
 - j. If the primary nurse-subject (who provided consent) takes a break and there is a temporary substitute nurse, we will turn off the display so that the investigational software cannot affect decision-making (except if the substitute nurse has been a nurse-subject for this study for a different ICU patient having completed the full protocol within the past 30 days; under that condition, we will continue the protocol during the break). If the primary nurse-subject break lasts longer than 60 min, we will terminate that enrollment.
 - k. The investigational software will be terminated one hour before the Technical Observer is scheduled to depart for the day, or one hour before the end of the consenting nurse's shift, or a maximum of 8 hours (whichever is shorter). After each subject enrollment, the apparatus will be removed from the care area and cleaned with an antibacterial wipe. The System hardware will be inspected to ensure there are no visible abnormalities such as evidence of spills or physical damage.

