For assessing technical operation, we will rely on (a) real-time error surveillance by the Technical Observer who watches the system during investigational use; the Technical Observer will document any unexpected technical issues in terms of run-time issues, connectivity issues, or any other issues; (b) Retrospective data review to ensure the completeness and accuracy of electronic data collected by the research software system; and (c) Analysis of log data the server log file and UI log file to confirm an absence of error-level and critical-level log statements.

We will generate descriptive statistics associated with (a) proportion of time that the patient’s BP is maintained within the goal range; and (b) descriptive statistics of the MAP prediction algorithm including mean prediction error, and also, clinical events that were associated with temporal windows with the highest prediction errors (i.e., top quartile of prediction error). The proportion of time that the patient’s BP is maintained within the goal range will be used for future study design. The results about the clinical events associated with the highest prediction errors will be used for potential future enhancements to the prediction methodology. We will review log files to confirm that there are no error- nor critical-level log events (except for those that are expected to naturally occur during system shut-down, which would be after each patient-subject data collection session has been completed).

As is routine for research studies, we will also aggregate subject characteristics in our analysis. These data will be obtained from the electronic medical record (EMR). Data will include routine demographics, co-morbidities, and clinical details of the index ICU stay such as clinical pathologies and clinical interventions. As this chart review is planned to occur at a time subsequent to the main investigational protocol, we will also record two patient identifiers (MRN and name) to ensure we have the correct identity of the subject. These identifiers will be digitally erased no later than 12 months after data collection has been completed. A hardcopy of the identifier will be kept by the PI in a locked cabinet in his MGH office for long-term storage, for any unforeseen need to re-identify the subjects for purposes of obtaining additional data from the EMR.

Power analysis (e.g., sample size)

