3. Annual Report is on file and completed in a timely fashion

C. Other documents / Investigator Site File (ISF):

1. CVs for all study staff are on file and updated every 2 years
2. Medical licenses for physician PI & Co-Investigators are on file and updated prior to expiration
3. Delegation Log is updated as new staff are added or removed from the study or new procedures are added
4. Financial disclosures for PI and relevant study staff are on file
5. Protocol is signed and understood by the PI
6. That information emails have been sent to Blake 12 ICU clinical staff to ensure awareness that System is limited by law to investigational use
7. Documentation exists that all software components have been tested and reviewed by users as per our specified software development procedures.
8. All other essential documents have been prepared and completed as appropriate

The completeness of the following **study documentation** will be verified after every 5 subjects or every quarter (whichever comes first):

D. Informed Consent:

1. Ensure that subject identification is on all pages of the ICF.
2. There is documentation that the subject is offered a copy of the consent form.
3. The subject and study representative signed and dated the consent form for him/herself.
4. Note to file made for any informed consent deviations.
5. Ensure a valid (current version date) copy of the consent form was used.
6. Ensure informed consent form is properly explained to and signed/dated by the study subject prior to participation.
7. Original informed consent form is retained by the investigators at the sites.

E. Protocol:

1. Confirm that the study staff is conducting the study in compliance with the protocol approved by IRB and if applicable, FDA.
2. The protocol deviations (exceptions and violations) are documented in the subject chart and reported to IRB as required.

F. Electronic Case Report Forms (REDCap):

1. Ensure the data reported on REDCap are complete.
2. Ensure that hourly BP and HR documented in REDCap by the Technical Observer are accurate, i.e., corresponds to data captured by the System within allowable tolerances (specifically, the System archive should span the documented BP and HR data in a time window +/- 5 min from the REDCap documented time of the observation).
3. Discrepancies between the source documents and REDCap are explained in a note to file or captured in a comment in REDCap.

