If any of these events occur, within 5 days, we will assess whether the event increased the patient-subject's risk of a serious adverse event. This assessment will include conferring with the study PI; the Blake 12 intensive care unit chief; and the Blake 12 intensive care unit nursing leader, to evaluate whether the event represented an event that is more than minimal risk to future subjects. If any of these (the study PI; the Blake 12 intensive care unit chief; and the Blake 12 intensive care unit nursing leader) judges that the event poses more than minimal risk to future subjects, we will halt the study.

Outcomes monitoring

As detailed above, the independent monitor will evaluate the outcomes data, including the completeness of all data collection instruments; the accuracy of the system software archive (based on a comparison with the Technical Observer's hourly annotation of vital signs); and the presence of time-stamped software logs for each enrolled patient-subject.

Adverse event reporting guidelines

Adverse event means any untoward medical occurrence associated with the use of an intervention in humans, whether or not considered intervention-related (21 CFR 312.32 (a)).

We will rely on the system data archive; annotations by the Technical Observer; and interview responses by the nurses to reveal adverse events. Adverse events will include all sustained hypotension episodes (as per Section 3.2.2.1 of this IDE Application); tachyarrhythmias (HR > 150 bpm) or bradyarrhythmias (HR < 50 bpm) that persist for more than ten minutes; needs for chest compressions or defibrillation; or any unscheduled bedside response by the ICU care team involving more than the patient's primary nurse.

An adverse event (AE) or suspected adverse reaction is considered "serious" if, in the view of the investigator/sponsor, it results in any of the following outcomes: death, a life-threatening adverse event, inpatient hospitalization or prolongation of existing hospitalization, a persistent or significant incapacity or substantial disruption of the ability to conduct normal life functions, or a congenital anomaly/birth defect. Important medical events that may not result in death, be life-threatening, or require hospitalization may be considered serious when, based upon appropriate medical judgment, they may jeopardize the participant and may require medical or surgical intervention to prevent one of the outcomes listed in this definition.

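### Does the ±5 min archive check in P.9 item F.2 leave the minute-level event times of P.5 step i unprotected?

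*Combined protocol and SAP*

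**What the plan says.** P.9, item F.2, tells the independent monitor to confirm the hourly BP and HR that the Technical Observer enters in REDCap. The rule is that "the System archive should span the documented BP and HR data in a time window +/- 5 min" of the recorded time. Outcomes monitoring in P.9 uses the same comparison to judge "the accuracy of the system software archive (based on a comparison with the Technical Observer" and the hourly annotations), and also asks for "the presence of time-stamped software logs for each enrolled patient-subject".

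P.5, step i, deals with clinical events. When hemodynamics change substantially, "a time-stamped annotation will be made for the perceived cause", and the goal is timing "down to the precise minute that the events occur". The clock is not named.

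P.6, Statistical methods, describes "clinical events that were associated with temporal windows with the highest prediction errors", meaning the top quartile of error. The result "will be used for potential future enhancements to the prediction methodology". The window length is not given. P.6 also promises "Retrospective data review to ensure the completeness and accuracy of electronic data collected by the research software system" without stating a method.

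**The concern.** The P.6 description joins two time records: event annotations by the observer, and archived vital signs with forecasts by the System. If different clocks stamp them, the join is only as good as their agreement. F.2 is the only stated check that sets an observer-recorded time against archive time, and its window is 10 min wide in total. Item F.6 asks whether certain events were captured, not when. Outcomes monitoring asks that time-stamped logs exist, not that clocks agree.

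An unnoticed difference of 4 to 5 min would be four to five times the one-minute goal. It would also be 4/10 to 5/10, or 40 to 50%, of the 10-min average forecast lead quoted in P.1. An intervention could then appear in the record after the prediction error that it caused, and a later revision of the algorithm could be misinformed.

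**Working it through.** **Inputs from the documents.** Tolerance ±5 min (P.9, F.2); event timing goal 1 min (P.5, step i); 20 sessions (P.6, Power analysis); 4 to 8 h per session (P.5, Data to be collected); observation at least every 15 min (P.5, step g). The ±5 min tolerance is a chosen rule with no derivation, so there is no plan figure to reproduce.

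**1. What F.2 can see, by logic.** Let the REDCap clock differ from the System clock by d minutes. If the reading is an archived value and its recorded time is otherwise exact, its true archive time lies inside the window whenever |d| ≤ 5. The reading then lies between the window's minimum and maximum and passes. Hourly readings give 20 × 4 = 80 to 20 × 8 = 160 time points, and all of them would pass. No BP model is needed.

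**2. Readings that fall between archive samples.** This needs assumptions that the documents do not supply: first-order autoregressive BP, correlation time 1 to 60 min, archive interval 5 or 60 s, values unrounded or rounded to 1 mmHg with SD 4 or 8. Simulated pass rates for a reading midway between samples:

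| Archive interval | d = 0 | d = 4 min | d = 5 min |
|---|---|---|---|
| 60 s | 0.853–0.980 | 0.840–0.963 | 0.705–0.890 |
| 5 s | 0.989–1.000 | 0.986–1.000 | 0.917–0.992 |

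The largest drop from 0 to 4 min is 0.905 − 0.842 = 0.063. Over the study that is 0.063 × 80 = 5 to 0.063 × 160 = 10 extra flags per variable. The largest drop from 0 to 5 min is 0.905 − 0.709 = 0.196, or 0.196 × 80 = 16 to 0.196 × 160 = 31 flags. So F.2 carries some timing information in the sparse-archive case. The failure rate with aligned clocks is unknown, however, so a clock difference could not be read off the flags.

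**3. What an offset would do to P.6.** If an event falls uniformly within a window of w minutes, an offset d moves it to another window with probability min(1, d/w).

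| Offset | w = 1 | w = 5 | w = 10 | w = 15 | w = 60 |
|---|---|---|---|---|---|
| 3 min | 1.00 | 0.60 | 0.30 | 0.20 | 0.05 |
| 5 min | 1.00 | 1.00 | 0.50 | 0.33 | 0.08 |

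The effect depends mainly on w, which the analyst has yet to choose.

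**4. Would tightening F.2 help?** In a second simulation (10-s archive, SD 8 mmHg, time constant 5 to 60 min, all assumed), a ±1 min window passes every reading at offsets of 0 to 1 min, 59–84% at 2 min and 43–72% at 5 min. It would react to timing, but equally to values entered more than about a minute late. That would spoil its use as a screen of hand-entered values.

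**5. Would a mean signed difference help?** With k readings in each of 20 sessions and intraclass correlation ICC, its 95% half-width, in SDs of the paired differences, is t(0.975, 19) × √[(1 + (k − 1)ICC)/(20k)], with t = 2.093. For k = 8 and ICC = 0: 2.093 × √(1/160) = 0.165. For k = 4 and ICC = 0: 2.093 × √(1/80) = 0.234. For ICC = 1: 2.093 × √(1/20) = 0.468. These figures concern a constant BP offset. For a signal without trend, a pure clock shift has an expected mean difference of zero, so the statistic would not measure timing.

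**The case for a change.** The best case for a change is that a clock comparison takes seconds and must be made during the session. Without it, later realignment would use the BP response to place the event, which is circular when the question is which events accompany BP prediction errors. The sponsor also intends to use the result. This stands as a reason for good practice at the bedside. It does not show that a stated rule gives a wrong answer.

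Three points weaken it:

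- Nothing in the documents suggests that the clocks differ by minutes. The 4 to 5 min figure is the edge of what F.2 can miss, not an estimate.
- Matching clocks would not by itself secure minute-level times. Step g permits gaps of up to 15 min between observations, and step i bars the observer from asking for clarification during time-sensitive care. Late entry could therefore exceed any clock difference that F.2 misses, even if the System itself stamped the annotations.
- The annotation records a perceived cause of a change seen at the bedside, so the link between event and BP does not rest on time stamps alone.

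The protocol also refers to parts of the IDE application and to software testing records that were not supplied. A clock procedure may be set out there.

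**Conclusion.** No change to the plan follows. F.2 is a reasonable gross screen for hourly values and for the archive, and its tolerance is a fair allowance for hand entry. It is nowhere presented as a test of clock agreement. It is true that differences of up to about 5 min would largely pass it. With an exact recorded time and an archived reading this is certain; the other pass rates rest on the assumed BP models.

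What is left is missing detail: which clock stamps the annotations, and how long the P.6 windows are. A competent team would note the clock source when running sessions, choose the window with the timing uncertainty in mind, and report both with the result. The exposure is confined to one exploratory description meant to suggest later improvements. The questionnaire results and the choice of 20 sessions do not depend on it. Mean prediction error, time in goal range and arrhythmia durations do not depend on it either, provided that they are computed on the archive's own clock.

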- g. Active use of the System will be observed by a Technical Observer, i.e., an IRB-approved member of the investigative team. The Observer will generally observe the system continuously, with a minimum of at least one observation every 15 minutes. These observations provide additional assurance that there is no potential interference with any other aspect of the patient's care; that the technical performance of the System is grossly consistent with its intended operation; to ensure that the patient doesn't express any concern; and to ensure that the nurse doesn't express any concern. By protocol, if the nurse, patient, or patient family member states any negative perception of the investigational system, the Technical Observer will ask whether the nurse/patient/family member prefers the protocol to stop, and will oblige if this is requested. If the protocol is stopped early by request of the nurse, patient, or family member, the Technical Observer will ask for feedback after stopping the protocol and removing the apparatus: "You requested that we stop our testing protocol. Can you tell us why, to help us ensure that this testing protocol is safe and appropriate for other ICU patients?" The protocol will also terminate early if an Exclusion criterion is met: receiving two simultaneous vasopressors running at maximum doses (per the ICUs own protocols) or who is on one maximum-dose vasopressor and has a contraindication to receiving a second vasopressor (e.g., insufficient vascular access). During the protocol, the nurse will have the option to adjust the Index Threshold per their clinical practice preferences, and the Technical Observer will provide technical support of the nurse decides to do this. Lower thresholds for the Index Threshold provide higher sensitivity and earlier warnings at the expense of reduced positive predictive value. Higher thresholds the Index Threshold provide lower sensitivity and less advanced notifications at the benefit of

higher positive predictive value. Within the second hour of the protocol session, the Technical Observer will explicitly confer with the nurse about the operation of the system, confirming whether the nurse understands the visual display elements, whether the nurse would like to adjust the Index Threshold, and whether the nurse has any concerns about the investigational display or the protocol. This check-in will occur at a time when the nurse is not occupied with direct patient care.

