4. Ensure that the data reported in REDCap from each nursing-subject interview are complete.
5. Ensure that the log files for each patient-subject session do not include any error- or critical-level message (except for those that are expected to naturally occur during system shut-down, which would be after each patient-subject data collection session has been completed).
6. Ensure that any event note for the patient's ICU documentation record that involved more than the primary nurse as a clinical responder was captured by the Technical Observer's annotations.

Safety monitoring

After the first 5 subjects are enrolled, the nurse-subject responses to the questionnaire will be submitted to the IRB, along with a report of any adverse events.

The following events represent possible adverse events:

- (a) the Technical Observer (a member of the research team) identifies any failure of the software and terminates the session (the Technical Observer may also terminate for any subject reason related to any subjective perceived negative impact on the subject's care);
- (b) if the nurse indicated that the protocol was having any negative effect on the patient's care, either during the execution of the protocol session, or in responses to the questionnaire that is conducted after every enrollment ("Question 3: Did you identify any output by the system that is dangerously confusing, or dangerously inaccurate? If so, what?"; and "Question 4: This system provides lots of visual information, which might be distracting. At any time, did the system actually distract you from noticing something important about your patient or administering important care to your patient, such that your response to the patient was delayed?");
- (c) if the patient/close family member indicated any discomfort with the protocol session.
- (d) Review of the software logs indicates any error-level or critical-level log statements were generated.

(e) Review of the software data archive indicates any interruption in the routine monitoring of vital-signs.

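### Safety trigger (a) counts a software failure seen by the Technical Observer only if the session is also ended, so a fault seen without termination is assessed only if another trigger catches it

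*Combined protocol and SAP*

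**What the plan says.** **P.9, Safety monitoring.** Five events count as possible adverse events. In (a), the Technical Observer "identifies any failure of the software and terminates the session". A parenthesis adds that "the Technical Observer may also terminate for any subject reason related to any subjective perceived negative impact on the subject's care". Event (b) applies "if the nurse indicated that the protocol was having any negative effect on the patient's care", whether during the session or in the questionnaire. Event (c) is discomfort expressed by the patient or close family. Event (d) is: "Review of the software logs indicates any error-level or critical-level log statements were generated". Event (e) is: "Review of the software data archive indicates any interruption in the routine monitoring of vital-signs".

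**P.9, consequence.** "If any of these events occur, within 5 days, we will assess whether the event increased" the patient's risk of a serious adverse event. The PI, the unit chief and the unit's nursing leader are consulted, and the study halts if any one of them sees more than minimal risk to future subjects.

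**P.6, Statistical methods.** For the technical-operation analysis, "the Technical Observer will document any unexpected technical issues in terms of run-time issues, connectivity issues, or any other issues".

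**P.5, step g.** A session can be stopped at the request of the nurse, patient or family. In addition, "The protocol will also terminate early if an Exclusion criterion is met", and the vasopressor criterion is then named. Software failure is not mentioned as a reason to stop.

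**The concern.** The list (a) to (e) is the entry to the only assessment in the plan that can halt the study for a device problem. The Observer is the person placed at the bedside to notice such problems. Yet a fault that the Observer sees counts under (a) only when the session is also ended, while one error-level log line counts under (d) with no such condition. Direct human observation thus faces a stricter test than a log entry, and the protocol gives no reason for this.

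At stake is the completeness of the formal safety review. The Observer belongs to the research team, and P.1 declares that investigators invented the software. Entry to the assessment is better tied to the occurrence of a fault than to a team member's decision about ending the session.

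**Working it through.** No arithmetic applies: the plan gives no failure rate, and the question is one of wording. The check treats (a) to (e) as alternatives, any one of which starts the assessment, and asks whether a fault that the Observer has seen can miss all five.

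**Step 1: what (a) requires.** The sentence needs both a failure identified and a session terminated. The parenthesis adds a further reason to terminate. It does not bring in failures without termination.

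**Step 2: does a failure always end the session?** If it did, the second condition would be harmless. No section says so. Step g covers requests and an exclusion criterion, step j a long nurse break, and step k the scheduled end.

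**Step 3: is there another route to the assessment?**
- The P.6 record of technical issues feeds the technical-operation analysis. No link to the assessment is stated.
- The adverse event guidelines in P.9 use Observer annotations as a source, but the events they list are clinical: sustained hypotension, arrhythmia, resuscitation and unscheduled multi-clinician response.
- The independent monitor checks REDCap completeness, hourly vital signs, nurse interviews, log files and event notes. No item asks whether a technical annotation reached the assessment.

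**Step 4: case check.** The Observer sees a fault and the session continues, so (a) is not met in any row.

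| Feature of the fault | Trigger met | Assessed within 5 days? |
|---|---|---|
| Writes an error- or critical-level log statement | (d) | Yes |
| Leaves a gap in the archive | (e) | Yes, if the gap counts as an interruption in monitoring |
| Nurse reports a negative effect on care | (b) | Yes |
| Patient or family expresses discomfort | (c) | Yes |
| None of the above | none | No |

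Only the last row escapes. A stale or wrong screen could fall there: the archive and the display are different things, and a display fault need not interrupt the archive or write an error line.

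**Step 5: how far (b) helps.** Event (b) needs no termination, and every nurse is asked about confusing or inaccurate display output (Question 3A in P.5). However, the version of Question 3 reproduced in P.9 asks only about output that is dangerously so. A plain yes to 3A is therefore not clearly a trigger.

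**The case against.** The strongest case is that (a) describes a sequence: a failure is seen, so the session ends. The word for an additional termination in the parenthesis fits this, because it treats the software-failure termination as the ordinary one. No section describes the Observer working around a failure and carrying on. Step g is also not a closed list of reasons to stop, since steps j and k add others, so its silence on software failure is not a contradiction.

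This makes the sequential reading possible, but the text does not state it. If it is what was meant, the rule that failure ends the session is missing from the procedures. Either way the sections need to be reconciled.

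The other safeguards are also real. The nurse can raise a problem at any time, is asked about the display within the second hour (step g), and completes the questionnaire. Events (d) and (e) cover many faults. These points stand, and they make the gap small.

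Two stronger readings are tempting and are not supported:
- A reader might infer that a system restarted in mid-session would escape review. That is among the cases most likely to be caught. The plan expects error-level messages at shut-down, (d) carries no exemption for them, and the exemption stated elsewhere covers only shut-down after the session. A restart may also leave an archive gap. The protocol describes no restart procedure, so how one would appear is an assumption.
- A reader might infer that the PI hears of a fault only if the session is ended. The PI conducts at least the first session, is reachable during all of them, and the Observer's annotations are study data. What is missing is the stated route into the formal assessment with the unit leaders.

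Finally, P.7 refers device malfunctions to Section 4 of the IDE application, which is not among the documents. A rule on failure handling may be there.

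**Conclusion.** The point holds in a narrow form. As written, an Observer-identified failure without termination is assessed only if (b), (c), (d) or (e) also applies. One class is left out: faults seen at the bedside, with no error-level log line, no archive gap and no complaint. For that class no trigger applies, but this follows from how the class is defined and says nothing about how often it would occur. With no failure rate in the plan, frequency cannot be estimated.

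The conclusion assumes that the conjunction in (a) is meant literally and that no rule outside these documents closes the gap.

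Two limits apply. A reader might extend the point to failures that nobody notices, but rewording (a) would not reach those. A reader might also count an implausible forecast as a failure, but P.6 treats prediction error as a quantity to be described, so a poor forecast is not clearly a software failure.

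Minor; a cheap improvement.

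**What to change.** - In P.9, reword (a) so that it applies when the Technical Observer identifies any failure of the software, whether or not the session is then ended. Make Observer termination for a perceived negative impact on care a separate trigger.
- In P.6, add one sentence saying that an Observer annotation describing a software failure is passed to the 5-day assessment in P.9.
- Reconcile P.5 step g with P.9 on termination initiated by the Observer. Which stopping rule should apply is for the investigators to decide; the two sections should state the same one.

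The cost is about three sentences. The burden is likely to be a few more items, over 20 sessions, for an assessment that already exists. The change affects what is reviewed, not how patients are managed.
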